#### 6.1.4.1.2 Imputation for supplemental estimand

Based on the feedback from FDA, the originally pre-specified primary analysis estimand will remain unchanged, but will be re-labeled as a supplemental estimand and will handle all intercurrent events using a “Treatment Policy Strategy” (Section 8.1.1). Imputation for the supplemental estimand will be similar to the process described above for the primary estimand; however, subjects who discontinue due to lack of efficacy or adverse event will be treated the same as those who did not discontinue for one of those reasons. All observed data for these subjects will be included in the imputation process subject to the analysis visit window strategy described in Section 6.1.5.

#### 6.1.4.2. Tipping Point Analysis

The sensitivity analysis for the primary endpoint will be performed by using a specified sequence of shift parameters. The range of shift parameters to be included in this analysis are 0 to 2 by 0.5 for active and -2 to 0 by 0.5 for Vehicle. Once the approximate point of the shift is determined, the analysis will be rerun using an expanded range around the approximate tipping point, to determine the tipping point with greater precision (i.e., to 2 decimal places, by 0.01). Thus, the value at which the results of the primary analysis are shifted from significant (i.e.,  $\alpha \leq 0.01$ ) to non-significant (i.e.,  $\alpha > 0.01$ ) will be determined.

Steps 1 and 3 of the analysis will be the same as for the multiple imputation analysis as described in [Section 6.1.4.1.16.1.4.1](#). However, Step 2 of the analysis is where the shift parameters will be applied. Pseudo-code for Step 2 is as follows:

```
proc mi data=example_1 seed=13698136 nimpute=15  out=example_2;
  by <Step 1 imputation number>;
  class <treatment> <site>;
  monotone regpmm(<baseline score> ..... <visit8 score>);
  var <treatment> <site> <baseline score> ..... <visit8 score>;
  mnar adjust( <visit2 score> / shift=YY adjustobs=(treatment ='Roflumilast
  Foam 0.3%));
  mnar adjust( <visit4 score> / shift=YY adjustobs=(treatment =
  'Roflumilast Foam 0.3%));
```

```

mnar adjust( <visit8 score> / shift=YY adjustobs=(treatment =
  'Roflumilast Foam 0.3%'));
mnar adjust(<visit2 score> / shift=ZZ adjustobs=(treatment='Vehicle
  Foam'));
mnar adjust(<visit4 score> / shift=ZZ adjustobs=(treatment='Vehicle
  Foam'));
mnar adjust(<visit8 score> / shift=ZZ adjustobs=(treatment='Vehicle
  Foam'));

run;

YY and ZZ will encompass all combinations of the range of shift parameters as
pre-specified above.

```

Imputed values for subjects who discontinue due to lack of efficacy or adverse event will be handled as described in Step 2 of Section 6.1.4.1.1 to ensure that these subjects are analyzed as non-responders at all visits on or after discontinuation of treatment.

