### **Figure 1: Primary and Secondary Endpoint Testing**

## 6.1.4. Handling of Dropouts or Missing Data

### 6.1.4.1. Imputation of Missing Data

#### 6.1.4.1.1. Imputation for the primary estimand

Any subject who prematurely withdraws from the study will have their last available data assigned to an analysis window as described in [Section 6.1.5](#). To comply with the definition of the primary estimand (Section 8.1.1), data collected on or after the date of last dose for subjects who discontinue due to lack of efficacy or adverse event will be removed from the source data used for multiple imputation process. WI-NRS weekly averages will be removed from the source data used for multiple imputation if the day of last dose falls within the day interval used for the weekly average as defined in Section 6.1.5. This procedure will ensure that the data collected after intercurrent events are not used in the imputation process.

For the primary efficacy endpoint of IGA score, the primary analysis will impute missing values using a regression-based multiple imputation model.

This is a three-step process.

1. The first step is to understand the pattern of missingness. In order to perform the multiple imputation, a monotone missing pattern must be achieved. For example, if there exist values for baseline and Week 8 visits, but missing values for the Week 2 or 4 visits, Markov-Chain Monte-Carlo (MCMC) method will be used to impute the small amount of missing data that may be missing at the intermediate visits that is required to make the missing data pattern monotone before applying the multiple imputation algorithm. This method uses a non-informative Jeffreys prior to derive the posterior mode from the expectation-maximization (EM) algorithm as the starting values for the MCMC method. This MCMC method will use seed of 81054655. The IGA score will be treated as a continuous variable for this step. To avoid values that could not be observed in practice, imputed values will be constrained to be integers in the range of 0 to 4. Total of 10 imputations are done in the MCMC step.

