2. Once the monotone pattern is achieved, the next step is to implement the imputation algorithm. For this, the Predictive Mean Matching method (PMM) will be used. This method is particularly helpful if the normality assumption is violated. For subjects with complete data up to a particular visit, a PMM model will be fit that includes the outcome at that visit as the dependent variable and as independent variables, treatment group, and pooled site using a seed of 13698136. This process will be repeated 15 times, resulting in a total of 150 complete analysis datasets. The seed may be changed after unblinding in case of any issues with the imputation process, and it will be documented in the CSR if any change is required. For subjects who discontinue due to lack of efficacy or adverse

event, data from analysis visits that occurred or would have occurred after discontinuation will be replaced with the baseline value. As a result, these subjects will be defined as non-responders for all analyses at these specific analysis visits.

3. For each completed dataset, compute the necessary derived variables. The dichotomous success rate (IGA score of ‘clear’ or ‘almost clear’ plus at least 2-point improvement) will be derived. The results obtained will be analyzed using the Cochran-Mantel-Haenszel (CMH) analysis for each of the complete analysis data sets stratified by baseline IGA score and pooled site as described in Section 6.1.6. The results will be combined into one multiple imputation inference (odds ratio, associated confidence interval and p-value) using PROC MIANALYZE as illustrated (Ratitch 2013).

This approach to imputation should be superior to other strategies such as carrying forward the last available observation, which may yield unrealistic imputed values. Also, the use of multiple imputation avoids the problem of artificially increasing power through data imputation associated with single-imputation methods because it accounts for the uncertainty associated with the imputation. The multiple imputation is performed for ITT population only. The analysis for the mITT Population will use the MI datasets already created for the ITT population (i.e., no new MI datasets will be generated).

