Similar multiple imputation procedure will be implemented for tested secondary endpoints as primary endpoint. Other missing data will not be imputed, with the exception of incomplete dates as described in [Section 6.1.8](#). For responder analysis, only observed data will be used. Only observed data will be summarized using descriptive statistics.

The SAS pseudo code for the multiple imputation process is listed below:

Step 1:

```
proc mi data=example seed=81054655 n impute=10 round=1 out=example_1;
  mcmc impute=monotone;
  var <baseline score> ..... <visit8 score>;
run;
```

Step 2:

```
proc mi data=example_1 seed=13698136 n impute=15 out=example_2;
  by <Step 1 imputation number>;
  class <treatment> <site>;
  monotone regpmm(<baseline score> ..... <visit8 score>);
  var <treatment> <pooled site> <baseline score> ..... <visit8 score>;
run;
```

Step 3: This step involves running CMH test stratified by pooled site and baseline IGA score on each completed dataset and combining the results using proc mianalyze.

```
Proc freq data=example noprint;
  by <imputationnumber> <visit> ;
  tables <pooled site>*<BL IGA>*<treatment>*<outcome>/ cmh alpha=0.01
COMMONRISKDIFF (TEST=MH cl=mh) ;
  output out=example_stat cmh;
run;
```

In order to apply PROC MIANALYZE, normalizing transformations must be applied to odds ratio. P-Values are obtained using Wilson Hilferty transformation as illustrated ([Ratitch 2013](#)).

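### The tipping-point analysis reports a tip to 0.01 on whole-number IGA grades, so the second decimal reflects how shifted scores are coded rather than how strong the missing-data assumption is

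*SAP*

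**What the plan says.** SAP 6.1.4.2 sets the shift parameters at "0 to 2 by 0.5 for active and -2 to 0 by 0.5 for Vehicle". Once an approximate tip is found, the analysis is rerun around it "to determine the tipping point with greater precision (i.e., to 2 decimal places, by 0.01". The pseudo-code applies the shifts inside Step 2 to the scores at visits 2, 4 and 8. It contains no rounding, minimum or maximum.

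The rest of the procedure is carried over: "Steps 1 and 3 of the analysis will be the same as for the multiple imputation analysis" (SAP 6.1.4.1.1). In that section:

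- Step 1 fills intermediate gaps, and "imputed values will be constrained to be integers in the range of 0 to 4". The matching code is "seed=81054655 n impute=10 round=1 out=example_1". This comes before any shift.
- Step 2 states that "the Predictive Mean Matching method (PMM) will be used". The method draws observed values, so an unshifted imputed IGA is a whole grade.
- Step 3 gives the success variable for each completed dataset: clear or almost clear "plus at least 2-point improvement) will be derived".

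SAP 8.1.1 says the IGA is reported in integers only, and that success equals clear or almost clear because everyone enters at grade 3 or 4. Subjects who stop for lack of efficacy or an adverse event are kept outside the shift "to ensure that these subjects are analyzed as non-responders at all visits on or after discontinuation of treatment".

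**The concern.** A fractional shift turns a whole grade into a score that the scale does not contain, and the SAP does not say explicitly whether such a score counts as almost clear. A binary outcome derived from whole grades can change only when a shift carries a grade across the success boundary. The position of that crossing within a half-grade step depends on the coding.

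The tip is meant to tell readers how far the missing values must depart from the model before significance is lost. A tip of +0.01 reads as extreme fragility and one of +0.50 as half a grade of tolerance. If coding alone separates the two, the reported number misleads. Among the analyses in SAP 8.1.3, this is the only one that varies the missing-data assumption by degree.

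**Working it through.** **Inputs.** Coarse grid, 0.01 step and shifted visits: SAP 6.1.4.2. Whole grades 0–4: SAP 8.1.1. Step 1 limits, matching and success rule: SAP 6.1.4.1.1. Sample of 300:150 and rates of 65% v 40%: SAP 3.2.

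**The plan's own figures.** The grid gives 5 × 5 = 25 pairs, and 10 × 15 = 150 completed datasets matches the SAP. The planning odds ratio reproduces: (0.65/0.35)/(0.40/0.60) = 2.786, stated as 2.79. The section states no expected tip.

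**Where success status changes.** Let g be the imputed Week 8 grade and d the shift, assumed to be added after the donor is drawn.

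- Score of 1 or less: success if g + d ≤ 1. In the active arm, g = 1 fails once d > 0 and g = 0 fails once d > 1. In the vehicle arm, g = 2 succeeds from d = -1 and g = 3 from d = -2.
- Half-up rounding: success if g + d < 1.5. In the active arm, g = 1 fails from 0.50 and g = 0 from 1.50. In the vehicle arm, g = 2 succeeds once d < -0.50 and g = 3 once d < -1.50.

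| Coding | Active jumps | Vehicle jumps |
|---|---|---|
| Score ≤ 1 | +0.01, +1.01 | -1.00, -2.00 |
| Half-up rounding | +0.50, +1.50 | -0.51, -1.51 |

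**Agreement.** At active 0, 0.5, 1, 1.5 and 2 the successful grades are {0,1}, {0}, {0}, none and none under both codings. At vehicle 0, -0.5, -1, -1.5 and -2 they are {0,1}, {0,1}, {0,1,2}, {0,1,2} and {0,1,2,3} under both. That is 5 of 5 per arm. On 0.01 steps over the whole range, the active arm differs from 0.01 to 0.49 and from 1.01 to 1.49, and the vehicle arm from -0.51 to -0.99 and from -1.51 to -1.99. That is 49 + 49 = 98 of 201 shifts per arm.

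**The 2-point rule read literally.** For baseline 3, a shifted 1.01 is an improvement of 3 - 1.01 = 1.99, a failure. So +0.01 in the active arm already fails every imputed almost clear in that stratum, while the vehicle arm has no direct change until -1.00. For baseline 4 the rule requires only a score of 2 or less, so the unstated grade rule decides. If the grade is rounded but the improvement is not, the first active jump is +0.01 for baseline 3 and +0.50 for baseline 4.

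**Between jumps.** Results move only if shifted Week 2 and Week 4 scores enter the later imputation models. A subject missing only Week 8 has no such movement.

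**Illustration.** One simulated dataset per missing rate, 300:150, with shifts +d active and -d vehicle. Assumed, not from the documents: monotone missingness, 5 donors, 7% at baseline 4, no site strata, 30 imputations. The tip is the first d with p > 0.01.

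| Missing | Observed success | Shift acts on | Tip, ≤ 1 | Tip, half-up |
|---|---|---|---|---|
| 20% | 66.1% v 43.3% | Week 8 only | 0.01 | 0.50 |
| 20% | same data | all visits | 0.01 | 0.50 |
| 15% | 64.9% v 41.8% | Week 8 only | 1.00 | 0.51 |
| 15% | same data | all visits | 0.9 | 0.51 |
| 10% | 64.3% v 43.2% | Week 8 only | 1.01 | 1.50 |
| 10% | same data | all visits | 1.00 | 0.51 |

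Away from the jumps d was searched every 0.1, so 0.9 means between 0.8 and 0.9. In the Week 8-only rows p is flat between jumps. In every row the two tips differ, yet both lie in the same half-grade step. For 15% with all visits shifted, p is 0.0074 at 0.5 and 0.060 at 1.0 under both codings.

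**The case against.** The strongest reply is that the text is not silent. Step 3 is unchanged, its 2-point rule fails a shifted 1.3 for anyone entering at grade 3, and SAP 8.1.1 equates success with clear or almost clear. With baseline at least 3, any score of 1 or less is an improvement of at least 2, whole number or not, so that equivalence holds under a cut at 1. Rounding appears only in Step 1. This stands: the literal text leans towards a cut at 1. It does not rescue the refinement, because that reading is the one in which +0.01 fails every imputed almost clear.

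Second, earlier-visit scores can feed forward, so results may drift between jumps. This also stands. With weaker simulated effects (57.5% v 43.2% at 10% missing, 57.7% v 41.8% at 15%), tips under rounding fell at 0.2 and 0.4. But the drift comes from re-matching donors and does not make a hundredth of a grade meaningful.

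Third, the table shells and programming notes are separate (SAP 15.1) and may contain a rule. They were not available, so the gap is in the SAP as written.

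A reader might infer that the whole tipping-point analysis is uninformative, or that the same data always give +0.01 under one coding and +0.50 under the other. Neither follows. The cut at 1 and half-up rounding give identical classifications on the coarse grid, and the illustration includes pairs such as 1.00 and 0.51, where the order reverses.

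**Conclusion.** The point holds for the 0.01 refinement. Direct success status changes at two shifts per arm, at places fixed by the coding, and the two codings differ at 98 of 201 fine shifts per arm. This part is exact, given whole-grade donors and a shift added after matching. The second decimal therefore does not measure the strength of the missing-data assumption.

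The consequence is limited. This is one of seven sensitivity or supplemental analyses of the primary endpoint in SAP Table 6. The primary test, alpha and sample size are untouched, so a reader should not infer that the primary result is in doubt.

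Whether a tip occurs at all depends on missing rates that the documents do not give. In a separate simulation at the planning rates, the median p at the extreme corner (+2 active, -2 vehicle) was 0.0007, 0.025, 0.24 and 0.51 at 5%, 10%, 15% and 20% missing. With only the active arm shifted, the median did not cross 0.01 at 5–10% missing (largest 0.0021). Those runs assume 45% of successes are clear, 30 pooled sites, 10% severe at baseline, 5 donors and data missing at random. They show a range, not a prediction.

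**What to change.** In SAP 6.1.4.2:

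- Delete the rerun by 0.01.
- State that a shifted score of 1 or less counts as success, with shifted scores limited to 0–4.
- Report the two-way table of pooled p-values on the pre-specified half-grade grid. Interpret it at whole-grade shifts (active 0, 1, 2; vehicle 0, -1, -2), where every shifted score, once limited, is a real IGA grade.
- Keep lack-of-efficacy and adverse-event discontinuations as non-responders.

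Replacing the 25-pair grid with a 3 × 3 table is not needed, since stating the rule and dropping the refinement cure the defect.

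The cost is re-programming one sensitivity table (14.2.1.2.5) and a coarser reported tip, with no new data. SAP Version 3.0 already post-dates unblinding, so the clinical study report must label the change as made after unblinding.

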### 6.1.5. Analysis Visit Windows

Visits will be analyzed as scheduled. Unscheduled, early termination visits, and/or repeated measurements will only be included if a scheduled measurement is not available, and the early termination or unscheduled/repeated measurement falls within the analysis visit windows as described in [Table 2](#). Unscheduled/repeated measurements will be listed.

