### **9.4. Vital Signs**

Descriptive summaries of observed values and changes from baseline will be calculated for systolic blood pressure, diastolic blood pressure, heart rate, height, weight, body mass index and oral body temperature by treatment group and visit.

Changes in weight by treatment group will summarize the number of subjects who gain or lose  $\geq 5\%$  of their baseline body weight during the course of the study, as well as subjects who gain or lose  $\geq 10\%$  of their baseline body weight over the course of the study by treatment group and visit.

BMI is derived as specified in [Section 6.1.7](#). Shift tables (overall, subjects who indicated weight loss was intentional and subjects weight loss was not intentional at each visit) by treatment group for subjects who shift from their baseline BMI category (underweight, normal, overweight, obese) to a different BMI category throughout the course of the study will be provided by treatment group and visit.

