### **9.5. PHQ-8 and Modified PHQ-A**

PHQ-8 will be completed by adult subjects and modified PHQ-8 is filled by adolescent subjects of age 12-17 years inclusive. Data for PHQ-8 and Modified PHQ-A will be classified using each subject's total score at a time point into a category based on the following scoring system:

- None – Minimal depression (0 to 4)
- Mild depression (5 to 9)
- Moderate depression (10 to 14)
- Moderately severe depression (15 to 19)
- Severe depression (20 to 24)

Shift tables showing the category of severity at each time point by treatment group will be presented.

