## **9.6. CDI-2**

Parents/caregivers will complete the CDI-2 for subjects belonging to 9-11 years of age inclusive. For Children’s Depression Inventory 2(CDI-2), descriptive summaries of observed values and changes from baseline will be calculated for the total score and the 2 scales emotional problems and functional problems by treatment group and visit.

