14.3.3.1	Safety	Summary of Clinical Chemistry Laboratory Results (Standard Units) by Study Visit
14.3.3.2	Safety	Shift from Baseline in Clinical Chemistry Laboratory Results (Standard Units) by Study Visit
14.3.3.3	Safety	Summary of Hematology Laboratory Results (Standard Units) by Study Visit
14.3.3.4	Safety	Shift from Baseline in Hematology Laboratory Results (Standard Units) by Study Visit
14.3.3.5	Safety	Summary of Quantitative Urinalysis Laboratory Results (Standard Units) by Study Visit
14.3.3.6	Safety	Shift from Baseline in Quantitative Urinalysis Laboratory Results (Standard Units) by Study Visit
14.3.3.7	Safety	Summary of Qualitative Urinalysis Laboratory Results (Standard Units) by Study Visit
14.3.4.1	Safety	Summary of Vital Signs by Study Visit
14.3.4.2	Safety	Change in Weight from Baseline by Study Visit
14.3.4.3	Safety	Shift from Baseline in BMI by Study Visit
14.3.4.4	Safety	Change in Weight from Baseline by Study Visit – by Weight Loss Intentional/Non-Intentional
14.3.4.5	Safety	Shift from Baseline in BMI by Study Visit - by Weight Loss Intentional/Non-Intentional
14.3.5	Safety	Shift from Baseline in Patient Health Questionnaire (PHQ-8)/Modified PHQ-Adolescents by Study Visit
14.3.6	Safety	Summary of CDI-2 by Study Visit
14.3.7	Safety	Summary of Columbia-Suicide Severity Rating Scale (C-SSRS) Suicidal Ideation and Suicidal Behavior by Study Visit
14.3.8	Safety	Summary of Physical Examination by Study Visit
14.3.9	Safety	Summary of Concomitant Medications by Anatomic Therapeutic Chemical (ATC) Class Level 4 and Preferred Term
14.3.10	Safety	Summary of Pigmentation Assessment by Race
14.3.10.1	Safety	Shift from Baseline in Hypopigmentation by Study Visit
14.3.10.2	Safety	Shift from Baseline in Hyperpigmentation by Study Visit
14.4	Pharmacokinetic Data	
14.4.1	PK	Summary of Pharmacokinetic Concentration Results by Study Visit

\*Analyses of Scalpdex will be limited to subjects in the ITT population who have Seborrheic Dermatitis involvement on the scalp

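### Early-termination PHQ and CDI-2 scores taken after the Week 4 visit but by study day 42 enter no planned summary table

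*SAP*

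**What the plan says.** SAP 6.1.5 sits in the general statistical section and makes no exception for safety data. It states that "Unscheduled, early termination visits, and/or repeated measurements will only be included if a scheduled measurement is not available", and adds that the value must lie in a Table 2 window. Table 2 gives Week 2 study days 2–22, Week 4 days 23–42, and Week 8 day 43 onward. On what happens to the rest, the section says only "Unscheduled/repeated measurements will be listed", which does not name early-termination values.

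The safety sections then summarize by visit:

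- **PHQ (SAP 9.5):** "Shift tables showing the category of severity at each time point by treatment group will be presented". Table 14.3.5 is titled "Shift from Baseline in Patient Health Questionnaire (PHQ-8)/Modified PHQ-Adolescents by Study Visit".
- **CDI-2 (SAP 9.6):** descriptive statistics for "the total score and the 2 scales emotional problems and functional problems by treatment group and visit". Table 14.3.6 is titled "Summary of CDI-2 by Study Visit".
- **Weight (SAP 9.4):** counts of subjects gaining or losing at least 5% "of their baseline body weight during the course of the study", in a sentence that closes by asking for the result by arm and visit. The titles of Tables 14.3.4.2 and 14.3.4.4 both contain "Change in Weight from Baseline by Study Visit". Protocol 6.2.3 promises an on-study incidence of weight change above 5%.

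Under Protocol 5.5 the early-termination visit repeats the Week 8 procedures, so PHQ or CDI-2 and weight are all collected there.

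**The concern.** Protocol 2.4.2 names weight loss and psychiatric events as known effects of oral roflumilast and says this trial is designed to detect them. PHQ scores of 15 or more and CDI-2 scores of 32 or more are listed grounds for stopping product after consultation with a mental health professional (Protocol 4.8.6 and 5.9). The last score of someone who leaves the study early is therefore one that a safety reader would want to see tabulated.

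If the visit rule discards that score because a Week 4 score already fills the window, and no table reports the worst or any post-baseline value, the tables show only the earlier and possibly better score. What is at stake is the completeness of the PHQ and CDI-2 displays, not any inference: SAP section 9 plans no safety tests.

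**Working it through.** The plan states no figure on this point that could be reproduced. The check applies the written rule to possible visit days.

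**Inputs**

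- Study day = observation date − first dose date + 1 (SAP 6.1.7). Protocol Days 14, 28 and 56 are therefore study days 15, 29 and 57.
- Table 2 windows as given above.
- Visit tolerance: ±3 days at Week 2, ±5 days at Weeks 4 and 8 (schedule of visits).
- Post-baseline PHQ and CDI-2 are scheduled at Weeks 4 and 8 only. Weight is scheduled at every visit.

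**PHQ and CDI-2, with a scheduled Week 4 score in hand**

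An early-termination score on days 30, 35 or 42 falls in the Week 4 window, which is already filled, so it maps to no visit. On days 43 or 50 it maps to Week 8. The excluded days run from the day after the Week 4 visit to day 42:

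| Week 4 visit on study day | Excluded days | Number | Days before an on-target Week 8 visit | Share |
|---|---|---|---|---|
| 24 (earliest) | 25–42 | 18 | 32 (25–56) | 18/32 = 0.563 |
| 29 (on target) | 30–42 | 13 | 27 (30–56) | 13/27 = 0.481 |
| 34 (latest) | 35–42 | 8 | 22 (35–56) | 8/22 = 0.364 |

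If the Week 4 score is missing, an early-termination score on days 23–42 fills Week 4 and nothing is lost. Before Week 4 there is no gap for these scales, because Week 2 has no scheduled score to displace the value.

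**Weight, only if the counts are made strictly by visit**

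The same days apply after Week 4. After Week 2 the excluded days are 16–22 for an on-target visit (7 days), 13–22 for a visit on day 12 (10 days) and 19–22 for a visit on day 18 (4 days).

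**How many subjects**

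The documents do not say. As an assumption, let 1–3% of 450 subjects (4.5 to 13.5) have an early-termination visit after Week 4, with even timing:

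- On-target Week 4: 4.5 × 0.481 = 2.2 and 13.5 × 0.481 = 6.5.
- Extremes over the visit window: 4.5 × 0.364 = 1.6 and 13.5 × 0.563 = 7.6.

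These are displaced scores. The number worse than a score already tabulated would be smaller.

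**Does another provision rescue the value?**

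- Schedule footnote a sends early terminators for the Week 8 assessments. That fixes which procedures are done. SAP 6.1.5 names early-termination visits and places them by window.
- SAP 6.1.4.1.1 assigns withdrawn subjects' last data to a window, but it does so for imputation and defers to 6.1.5.
- SAP 6.1.8 promises that all collected data will be listed. The planned listings in SAP 14.3 name none for PHQ or CDI-2.

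**The case against.** The best case against is that almost nobody is affected and nothing promised is broken. Protocol 6.2 specifies no PHQ or CDI-2 analysis, and by-visit displays are a reasonable choice. An early-termination visit follows withdrawal from the study, for which Protocol 4.8.7 lists the subject's decision, death, loss to follow-up, or termination by the sponsor or a regulator. Death and loss to follow-up yield no questionnaire, and subjects who withdraw consent need not attend. The psychiatric and weight triggers in Protocol 4.8.6 stop product, not study participation, so those subjects can still supply a scheduled Week 8 score. High scores trigger referral whatever row they occupy. An event judged to be an adverse event that ends participation appears in Table 14.3.1.8. The general listing promise covers untabulated data. The table shells are a separate document that was not available. Any row added now is post hoc, and SAP section 1 already allows labelled post-hoc work.

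These points are accurate, and they are why the matter is minor. The 1–3% rate has no source in the documents, and the exemption for withdrawn consent points toward the low end. Some cases remain possible, because Protocol 5.9 also contemplates discontinuation from the study for an adverse event. None of the points puts the omitted score into a summary table, and a listing is not a summary.

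On weight the objection is stronger. The on-study wording of SAP 9.4 and Protocol 6.2.3 favours an any-time count, so exclusion is not established there. The by-visit ending and table titles leave it unclear.

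**Conclusion.** The point holds and is minor. Following SAP 6.1.5 as written, an early-termination PHQ or CDI-2 score obtained after a completed Week 4 assessment and by study day 42 appears in no planned PHQ or CDI-2 table. The span is 13 days for an on-target Week 4 visit and 8 to 18 days across the visit window. The number of subjects is unknown; about 2 to 7 is an illustration only. CDI-2 concerns only ages 9–11. Unscheduled visits add little, since Protocol 5.6 requires only adverse events and concomitant medications there.

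The conclusion rests on the SAP text and table titles, and the shells could change it. Weight handling is ambiguous, not shown to be wrong. The documents already use broader summaries elsewhere: Protocol 6.2.2 plans laboratory shifts to the worst post-baseline grade, and SAP 6.1.7 defines C-SSRS ideation on an any-time basis, although the C-SSRS table is also by visit.

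**What to change.** Keep SAP 6.1.5 for the by-visit rows and add a sentence saying that it does not restrict worst-value or any-time summaries. Then:

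- Add a worst post-baseline severity category row to Table 14.3.5.
- Add a highest post-baseline total score row to Table 14.3.6.
- State in SAP 9.4 that the 5% and 10% weight-change counts in Tables 14.3.4.2 and 14.3.4.4 include an any-time row using all post-baseline records, early-termination values included.
- Label these rows in the clinical study report as added after unblinding, since SAP version 3.0 itself postdates it.

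The cost is one sentence in each of two SAP sections and extra rows in four tables, from data already collected. The by-visit rows and all tests stay as they are.
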